### **5.0 DOSING DELAYS/DOSE MODIFICATION FOR TOXICITY**

Clinically significant adverse events or abnormal laboratory values assessed as unrelated to disease progression, intercurrent illness, or concomitant medications may require dose delay and/or dose modification. Such toxicities must have an attribution of possible, probable, or definite to encorafenib and/or binimetinib (see Section [9.3](#)). If multiple toxicities occur, dose modification decisions should be based on the most severe toxicity. If there is any question or clarification required concerning a toxicity, the treating site should contact the ABTC Central Office to determine patient's toxicity status. The ABTC Central Office, with the Study Chair (who may consult with Pfizer) will make the final decision.

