#### **5.1 Dose Modification for Encorafenib and Binimetinib**

The dose levels and the general approach to encorafenib and/or binimetinib dose modification on this trial are shown below. Adverse events (AEs) should be treated with the appropriate maximum supportive care, and dose reductions should be clearly recorded on the case report form.

Dose modifications are required for any clinically significant toxicity and are defined below.

- **In general, if toxicity occurs that is attributed to only one of the agents, only that agent should be dose-reduced/modified.**
- **If administration of binimetinib is interrupted, administration of encorafenib may be continued, but at a maximal dose of 300 mg per day.**

- If administration of encorafenib is interrupted, administration of binimetinib may be continued at the same dose
- If either binimetinib or encorafenib are permanently discontinued, the other drug should also be discontinued and the patient removed from the study.

If there is any question, [name] ([contact]) or [name] ([contact]) at the ABTC Central Office and the Study Chair should be contacted.

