Grade 3	
 
Treatment with encorafenib may be maintained or interrupted based upon the Investigator's discretion. Continue supportive measures, such as topical therapy, for symptomatic relief. Give instruction on life-style modifications.
 
 
If interrupted dosing of encorafenib per Investigator's judgment, interrupt until resolved to Grade <math>\leq</math> 1. Resume treatment with encorafenib at the same dose level or one reduced dose level based upon the Investigator's discretion.
 
1st or additional occurrence:  Interrupt dosing of encorafenib until resolved to Grade <math>\leq</math> 1. Promptly initiate supportive measures, such as topical therapy, for symptomatic relief. Give instruction on life-style modifications. Reassess the patient weekly. Then resume treatment at one reduced dose level of encorafenib.
 
 
Consider referral to dermatologist and manage HFSR per dermatologist's recommendation.
 
 
> 3rd occurrence:  Interrupt dosing of encorafenib until resolved to Grade <math>\leq</math> 1, decision to resume treatment with encorafenib at one reduced dose level or permanently discontinue encorafenib should be based upon the Investigator's discretion.

Nausea/Vomiting	
Grade 1-2	Maintain dose level of encorafenib and binimetinib. Promptly institute antiemetic measure.
Grade 3	Interrupt dosing of encorafenib and binimetinib until resolved to Grade $\leq$ 1. Then resume treatment at one reduced dose level of encorafenib. Resume treatment with binimetinib at the current dose if, in the judgment of the Investigator, the toxicity is considered to be unrelated to binimetinib, or at one reduced dose level. Note: Interrupt dosing of encorafenib and binimetinib for $\geq$ Grade 3 vomiting or Grade 3 nausea only if the vomiting or nausea cannot be controlled with optimal antiemetics (as per local practice).
Grade 4	Permanently discontinue encorafenib and binimetinib.
Other Adverse Reactions (including renal, hemorrhage).	
Recurrent Grade 2 or First occurrence of any Grade 3	Withhold encorafenib for up to 4 weeks. 
 
If improves to Grade 0-1 or to pretreatment/baseline levels, resume at one reduced dose level.
 
If no improvement, permanently discontinue.
 

First occurrence of any Grade 4	Permanently discontinue encorafenib or withhold for up to 4 weeks.

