Grade 1-2	Maintain dose level of encorafenib and binimetinib. Promptly institute antiemetic measure.
Grade 3	Interrupt dosing of encorafenib and binimetinib until resolved to Grade $\leq 1$ . Then resume treatment at one reduced dose level of encorafenib. Resume treatment with binimetinib at the current dose if, in the judgment of the Investigator, the toxicity is considered to be unrelated to binimetinib, or at one reduced dose level. Note: Interrupt dosing of encorafenib and binimetinib for $\geq$ Grade 3 vomiting or Grade 3 nausea only if the vomiting or nausea cannot be controlled with optimal antiemetics (as per local practice).
Grade 4	Permanently discontinue encorafenib and binimetinib.
Other Adverse Reactions (including hemorrhage)	
Recurrent Grade 2 or First occurrence of any Grade 3	Withhold for up to 4 weeks. 
 
If improves to Grade 0-1 or to pretreatment/baseline levels, resume at one reduced dose level.
 
If no improvement, permanently discontinue.
 

First occurrence of any Grade 4	Permanently discontinue or withhold for up to 4 weeks. 
 
If improves to Grade 0-1 or to pretreatment/baseline levels, then resume at one reduced dose level.
 
If no improvement, permanently discontinue.
 

Recurrent Grade 3	Consider permanently discontinuing.
Recurrent Grade 4	Permanently discontinue.

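### Both dose-modification tables give two different instructions for Grade 4 vomiting: interruption only if antiemetics fail (the Note in the Grade 3 row) and unconditional permanent discontinuation (the Grade 4 row)

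*Combined protocol and SAP*

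**What the plan says.** Section 5.1 has one table for encorafenib and one for binimetinib. Each has a Nausea/Vomiting block with rows for Grade 1-2, Grade 3 and Grade 4.

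In the encorafenib table, the Grade 3 row sets out interruption of both drugs until recovery and then resumption. It closes with "Note: Interrupt dosing of encorafenib and binimetinib for $\geq$ Grade 3 vomiting or Grade 3 nausea only if the vomiting or nausea cannot be controlled" (the sentence goes on to specify optimal antiemetics). The Grade 4 row beneath it reads "Permanently discontinue encorafenib and binimetinib".

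The binimetinib table repeats both lines, including the condition "only if the vomiting or nausea cannot be controlled with optimal antiemetics (as per local practice" and the unconditional Grade 4 row.

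Two general rules bear on the point:

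- Section 5.1, on permanent discontinuation: "If either binimetinib or encorafenib are permanently discontinued, the other drug should also be discontinued and the patient removed from the study".
- Section 5.0, on doubtful cases: "If there is any question or clarification required concerning a toxicity, the treating site should contact the ABTC Central Office". The Central Office, with the Study Chair, makes the final decision.

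**The concern.** The Note attaches an at-or-above sign to vomiting but gives nausea as plain Grade 3. Its wording therefore takes in Grade 4 vomiting, an event that also has its own row with a different and unconditional action. One event thus has two written instructions, and neither refers to the other.

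This is a stopping rule for both study drugs. A site that follows the Note could keep a patient on treatment, or only interrupt it, after a Grade 4 event. A site that follows the Grade 4 row stops both drugs for good. The difference bears first on patient safety. It also bears on time on treatment, and so on the opportunity to reach a response and have it confirmed at least 4 weeks later, as Section 8.1 requires.

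**Working it through.** No arithmetic applies; this is a comparison of text.

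**Inputs.** The Note in the Grade 3 row and the Grade 4 row of the Nausea/Vomiting block, in each of the two Section 5.1 tables; the general rules in Sections 5.0 and 5.1; the off-study rule in Section 10.2.

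**Step 1. What the Note covers.** For vomiting it covers Grade 3 and above. For nausea it covers Grade 3 only. The overlap with the Grade 4 row is therefore Grade 4 vomiting alone.

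**Step 2. The two instructions side by side.**

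| Event | Note in Grade 3 row | Grade 4 row | Same action? |
|---|---|---|---|
| Grade 4 vomiting, controlled by optimal antiemetics | No interruption | Both drugs stopped permanently | No |
| Grade 4 vomiting, not controlled | Interruption | Both drugs stopped permanently | No |
| Grade 4 nausea | Not covered | Both drugs stopped permanently | No overlap |
| Grade 3 vomiting or nausea | Interruption only if not controlled | Not covered | No overlap |

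The lines disagree in both Grade 4 vomiting cases. The widest gap, no hold against the end of treatment, arises only when antiemetics control the vomiting.

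**Step 3. Is it an isolated slip?** The same wording stands in both tables, so comparing one with the other does not settle it.

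**Step 4. Does anything else in the tables settle it?** There is no precedence statement. Nor do the tables treat Grade 4 uniformly:

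- Grade 4 uveitis, other eye disorders, dermatologic events and interstitial lung disease lead to permanent discontinuation.
- A first Grade 4 event under Other Adverse Reactions may instead be withheld for up to 4 weeks and resumed at one reduced dose level on improvement.
- Grade 4 asymptomatic CPK elevation is withheld for up to 4 weeks and binimetinib resumed at one reduced dose level on improvement.

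A site cannot conclude from the other rows that Grade 4 always means permanent discontinuation.

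**Step 5. What follows from permanent discontinuation.** Section 5.1 says that when either drug is permanently stopped, "the other drug should also be discontinued and the patient removed from the study". Section 10.2 keeps every patient in survival follow-up until death, and Section 10.0 requires adverse-event follow-up for at least 30 days after the last dose. What is lost is treatment and the chance of response on treatment, not survival data.

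**The case against.** The strongest reply is that the tables are meant to be read by grade. The Note sits inside the Grade 3 row, qualifies that row's interruption, and does not mention permanent discontinuation. A site that grades an event as 4 would go to the Grade 4 row and find a clear action. This is the more natural reading, and it stands as such. It does not remove the conflict, because it leaves the at-or-above sign with no function.

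A second reply is that Section 5.0 provides one central decision for doubtful toxicities, and Section 5.1 repeats the contact route. That also stands, and it limits divergence between sites. It works only if the site sees a question, and a site that reads one line alone may not.

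Stronger readings are tempting, but the documents do not support them:

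- *That the sign was placed on purpose to cover Grade 4.* Nothing shows intent. A drafting leftover is equally possible.
- *That the action is simply left to each site.* The central decision route argues against this.
- *That the Grade 4 row ends all participation.* The Section 5.1 wording on removal from the study suggests it, but Section 10.2 continues survival follow-up until death.
- *That the conflict is likely to arise.* Table 9-4 lists vomiting as likely (>20%), but for single-agent binimetinib and without a split by grade. With an assumed Grade 4 rate of 0.5% to 2%, the chance of at least one event among the maximum 62 patients would be 1 - 0.995^62 = 27% to 1 - 0.98^62 = 71%. For one 23-patient cohort it would be 1 - 0.995^23 = 11% to 1 - 0.98^23 = 37%. The assumed rate drives these figures and has no basis in the documents. They also ignore the requirement in Section 5.0 that the event be at least possibly drug-related, and whether antiemetics work. They cannot be used to size the problem.

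**Conclusion.** The inconsistency is real but narrow. On their wording, the Note and the Grade 4 row give different actions for Grade 4 vomiting in both tables, and no text says which governs. The row-by-row reading favours the Grade 4 row and central adjudication is available. The remaining risk is a site that acts on the Note alone and continues, or only interrupts, dosing where the Grade 4 row ends treatment.

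This rests on the printed wording, not on any assumed rate. How often it would arise cannot be estimated from the documents. No sample-size, power or error-rate figure is affected. A reader might infer a material effect on the 5-of-23 response threshold, but nothing in the documents allows that effect to be quantified. The point deserves correction because it concerns a stopping rule for both drugs and costs little to put right.

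**What to change.** Reconcile the Note and the Grade 4 row of the Nausea/Vomiting block so that exactly one instruction applies to Grade 4 vomiting, and use identical wording in the encorafenib and binimetinib tables. The edit may fall on the scope of the Note, on the Grade 4 row, or on both. Which clinical rule applies is for the sponsor's clinicians to decide, and this review takes no position on it.

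The cost is a short wording change in two tables. It needs no extra data, visits or patients and no change to the statistical design.

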### Recommended Binimetinib Dose Modifications \*

\*For adverse events that may be related to both encorafenib and binimetinib, guidance is provided for the other agent also.

For patients with pre-existing disorder resulting in AE >1, the new event must resolve to at least the pre-existing baseline to resume treatment following the prescribed rules as outlined in the Modification Table.

Severity of Adverse Event	Dose Modifications
Cardiomyopathy	
Asymptomatic, absolute decrease in LVEF of > 10% from baseline that is also below the LLN	Withhold binimetinib for up to 4 weeks, evaluate LVEF every 2 weeks. Resume binimetinib at one reduced dose level if the following are present: 
 
LVEF is at or above the LLN and
 
Absolute decrease from baseline is 10% or less and
 
Patient is asymptomatic.
 
 If LVEF does not recover within 4 weeks permanently discontinue binimetinib.
Grade 3-4 (Symptomatic congestive heart failure or absolute decrease in LVEF of > 20% from baseline that is also below LLN)	Permanently discontinue binimetinib. Closely monitor LVEF until resolution or up to 16 weeks.
Venous Thromboembolism	
Uncomplicated DVT or PE	Withhold binimetinib. 
 
If improves to Grade 0-1, resume at one reduced dose level.
 
If no improvement, permanently discontinue binimetinib.
 

Life threatening PE	Permanently discontinue binimetinib.
Serous Retinopathy	
Symptomatic serous retinopathy/ Retinal pigment epithelial detachments	Withhold binimetinib for up to 10 days. 
 
If improves and becomes asymptomatic, resume at the same dose.
 
If not improved, resume at one reduced dose level or permanently discontinue binimetinib.
 

Retinal Vein Occlusion (RVO)	

Severity of Adverse Event	Dose Modifications
Any Grade	Permanently discontinue binimetinib.
Uveitis	
Grade 1-3	If Grade 1 or 2 does not respond to specific ocular therapy, or for Grade 3 uveitis, withhold binimetinib and encorafenib for up to 6 weeks. 
 
• If improved, resume at same or one reduced dose level.
 
• If not improved, permanently discontinue binimetinib and encorafenib.
 

Grade 4	Permanently discontinue binimetinib and encorafenib.
Other Eye Disorders (i.e., Non-retinal Events, non-Uveitis Events)	
Grade 1-2	Maintain dose level of encorafenib and binimetinib and increase frequency of ophthalmic monitoring to at least every 14 days until stabilization or resolution.
Grade 3	Interrupt dosing of encorafenib and binimetinib and refer patient to ophthalmologist within 7 days. 
 
• If resolved to Grade <math>\leq 1</math> in <math>\leq 21</math> days, resume treatment at one reduced dose level of encorafenib and binimetinib.
 
• If not resolved to Grade <math>\leq 1</math> in <math>\leq 21</math> days, permanently discontinue encorafenib and binimetinib and close follow-up with ophthalmic monitoring until stabilization or resolution.
 

Grade 4	Permanently discontinue encorafenib and binimetinib and immediate follow-up with ophthalmic monitoring until stabilization or resolution.
Interstitial Lung Disease	
Grade 2	Withhold binimetinib for up to 4 weeks. 
 
• If improved to Grade 0-1, resume at one reduced dose level.
 
• If not resolved within 4 weeks, permanently discontinue.
 

Grade 3 or Grade 4	Permanently discontinue.
Hepatotoxicity	
Grade 2 AST or ALT increased	Maintain binimetinib dose. 
 
• If no improvement within 2 weeks, withhold binimetinib until improved to Grade 0-1 or to pretreatment/baseline levels and then resume at the same dose.
 

Grade 3 or 4 AST or ALT increased	See Other Adverse Reactions
Rhabdomyolysis or Creatine Phosphokinase (CPK) elevations	
Grade 4 asymptomatic CPK elevation or Any Grade CPK elevation with symptoms or with	Withhold binimetinib dose for up to 4 weeks. 
 
• If improved to Grade 0-1 resume at one reduced dose level.
 

Severity of Adverse Event	Dose Modifications
renal impairment	
 
If not resolved within 4 weeks, permanently discontinue binimetinib.
 

Dermatologic	
Grade 2	Implement supportive measures as above under encorafenib, dermatologic. If no improvement within 2 weeks, withhold until Grade 0-1. Resume at same dose if first occurrence or at one reduced dose level if recurrent.
Grade 3	Withhold until Grade 0-1. Resume at same dose if first occurrence or reduce one dose level if recurrent.
Grade 4	Permanently discontinue.
Nausea/Vomiting	
Grade 1-2	Maintain dose level of encorafenib and binimetinib. Promptly institute antiemetic measure.
Grade 3	Interrupt dosing of encorafenib and binimetinib until resolved to Grade $\leq 1$ . Then resume treatment at one reduced dose level of encorafenib. Resume treatment with binimetinib at the current dose if, in the judgment of the Investigator, the toxicity is considered to be unrelated to binimetinib, or at one reduced dose level. Note: Interrupt dosing of encorafenib and binimetinib for $\geq$ Grade 3 vomiting or Grade 3 nausea only if the vomiting or nausea cannot be controlled with optimal antiemetics (as per local practice).
Grade 4	Permanently discontinue encorafenib and binimetinib.
Other Adverse Reactions (including hemorrhage)	
Recurrent Grade 2 or First occurrence of any Grade 3	Withhold for up to 4 weeks. 
 
If improves to Grade 0-1 or to pretreatment/baseline levels, resume at one reduced dose level.
 
If no improvement, permanently discontinue.
 

First occurrence of any Grade 4	Permanently discontinue or withhold for up to 4 weeks. 
 
If improves to Grade 0-1 or to pretreatment/baseline levels, then resume at one reduced dose level.
 
If no improvement, permanently discontinue.
 

Recurrent Grade 3	Consider permanently discontinuing.
Recurrent Grade 4	Permanently discontinue.

## 5.2 Encorafenib and Binimetinib Dose Re-Escalation Guidelines

The lowest recommended dose level of encorafenib is 150 mg QD and the lowest recommended dose level of binimetinib is 15 mg BID. When the AE that resulted in a dose reduction improves to and remains stable at the patient's baseline level for a minimum of 14 days, the dose can be re-escalated to the next dose level at the discretion of the Investigator, provided there are no other concomitant toxicities that would prevent drug re-escalation. There is no limit to the number of times the patient can have their dose reduced or re-escalated, however:

- No dose re-escalation of encorafenib is allowed after a dose reduction due to prolonged QTc  $\geq 501$  msec
- No dose re-escalation of binimetinib is allowed after a dose reduction due to LVEF dysfunction
- No dose re-escalation of binimetinib or encorafenib is allowed after a dose reduction due to retinal toxicity  $\geq$  Grade 2.

Please refer to Dose Modification Table for recommended dose modifications for encorafenib and/or binimetinib, if applicable, based on the occurrence of treatment-related AEs. If a patient is re-escalated on a drug, please note this clearly on the case report forms and notify the ABTC Central Office that re-escalation is taking place.

## 5.3 Major Events

Major Events are non-treatment-related grade 3 and 4 hematologic and non-hematologic toxicities. Treatment should be delayed for major events if encorafenib and binimetinib may further complicate the non-treatment-related event. If a major event requires a delay of treatment, treatment must be delayed until toxicity is resolved ( $\leq$  grade 1 [or tolerable grade 2 for non-hematologic toxicity] or  $\leq$  baseline). If toxicity is not resolved in  $\leq 6$  weeks, the patient may be removed from treatment, pending discussion with the ABTC Central Office. The ABTC Central Office should be consulted if you are not clear on whether to continue or delay treatment.

## 5.4 Use of Hematologic Growth Factors

During the first 28 days of treatment, granulocyte colony stimulating factor (G-CSF) should be administered only for severe or prolonged neutropenia or for neutropenic sepsis. There will be no constraint on the use of growth factors during subsequent treatment; however, prophylactic use is discouraged and adherence to the American Society of Clinical Oncology (ASCO) guidelines is recommended (JCO, 12, 1994: pp 2471-2508). Patients should receive all necessary supportive care, including blood products, transfusions, antibiotics, pain medications, bisphosphonates, and replacement hormonal therapies (insulin, thyroid hormones, estrogen/progesterone).

## 5.5 Toxicity Criteria

All toxicities will be described and graded according to the NCI Common Terminology Criteria for Adverse Events (CTCAE) version 5.0. All appropriate treatment areas should have access to a copy of the CTCAE version 5.0. A copy of the CTCAE version 5.0 can be downloaded from the CTEP web site ([http://ctep.cancer.gov/protocolDevelopment/electronic\\_applications/ctc.htm](http://ctep.cancer.gov/protocolDevelopment/electronic_applications/ctc.htm)). See also Section [9.3](#), Recording of Adverse Events.

## 6.0 PHARMACEUTICAL INFORMATION

### 6.1 Encorafenib

**Other Names:** Braftovi, LGX818

**Information:** Encorafenib is manufactured by Pfizer and is supplied as hard gelatin capsules in a dosage strength of 75 mg. Encorafenib capsules consist of encorafenib drug substance, copovidone, poloxamer 188, succinic acid, microcrystalline cellulose, colloid silicon dioxide, crospovidone, and magnesium stearate of vegetable origin. The capsule shell is commercially available and contains gelatin and titanium dioxide as well as iron oxide red and yellow, ferrosulfuric oxide, and monogramming ink. The capsule has a beige cap with a stylized “A” and a white body on which is written “LGX 75mg”.

Encorafenib capsules should be stored at room temperature, not above 25°C and protected from moisture. Capsules are packaged in square, high-density polyethylene bottles that are induction sealed and closed with a polypropylene, child-resistant screw cap. Each bottle contains 90 capsules of Encorafenib. Encorafenib bottles will be labeled, at a minimum, with the lot number, contents (number of tablets), dosage strength, and storage conditions. Encorafenib should be dispensed to patients in the bottles provided by Pfizer and should not be repackaged at the site or pharmacy.

**Stability:** Refer to documentation enclosed with each shipment for expiration date. This is not included on the label for this product but will be provided with each shipment.

**Route of Administration:** Oral administration. Take encorafenib by mouth once daily with or without food. If a dose is missed, the dose can be taken if it is more than 12 hours until the next dose, otherwise it should be skipped.

